7.4.2 Saliva and Blood samples

BLOOD AND SALIVA SAMPLES SHOULD ONLY BE TAKEN ON A MONDAY, TUESDAY OR WEDNESDAY DUE TO THE TIME TAKEN TO SHIP AND PROCESS THE SAMPLES ON ARRIVAL AT THE LABORATORY.

A saliva sample will be taken from patients who have consented to the optional sub study. This will be taken at baseline for identification of germline DNA.

For patients taking part in this sub-study we will also request blood samples, up to 10ml each (for surrogate assays on platelet rich plasma, circulating mononuclear cells and free DNA studies) at screening, end of cycle 2, end of cycle 6, every 3 months for up to 1 year and end of treatment and/or progression. Collection tubes and appropriate transport will be provided

Once collected blood samples, saliva and tissue blocks should be processed as per the TORCH sample collection manual and sent to:

Oxford Molecular Diagnostics Centre

F.A.O [name]

Molecular Haematology

Level 4, John Radcliffe Hospital

[name]

[name]

Samples will be used for in-house molecular diagnostics and may also be sent to AstraZeneca for additional biomarker-related studies.

The Chief Investigator has overall responsibility for custodianship of the samples. Laboratories are instructed to retain any surplus samples pending instruction from the Chief Investigator on use, storage or destruction. It is possible that new or alternative assays may be of future scientific interest. At the end of the research study any surplus samples may be retained for use in other projects that

have received ethical approval. Hence, any surplus study samples may be transferred to a licensed tissue bank where they will be managed in accordance with applicable host institution policies and the Human Tissue Act (HTA) requirements. A patient may withdraw consent at any time. In this event, any samples and data that have already been provided for the research trial will be retained and used in the analysis. No further samples will be taken and any surplus material will be destroyed.

7.5 Dose Modifications

AZD2014 is expected to be well tolerated. Substantial toxicities should be managed as medically indicated and with temporary suspension of study drug, as appropriate. Dose reductions or holds and initiation of supportive care are allowed as clinically indicated by the treating physician. For each patient, a maximum of two dose reductions will be allowed. The reduced dose levels are presented in Table 1. If patients are unable to tolerate the 75mg bd dose of AZD2014, there is a possibility of changing to a continuous dosing regimen which may in some cases be better tolerated. This needs to be discussed with the chief investigator on a case by case basis.

Table 1.	AZD2014 dose level modification	
Dose level	AZD2014 PO daily dose	
Starting Dose	125 mg bd	
-1 Dose Level	100 mg bd	
-2 Dose Level	75 mg bd	

7.5.1 General dose modifications for toxicities

Dose reduction and discontinuation guidelines for haematologic and non-haematologic toxicities due to AZD2014 are shown in Table 2 and 3. Dose re-escalation is not permitted.

Table 2.	Dose modifications and discontinuation criteria for non-haematologic toxicities*

NCI CTCAE Toxicity Grade	Action
Grade 1, or 2	None
Grade 3 or 4 and/or clinically significant	
Expected manageable/reversible with dose reduction	Hold study drug until meets one of the criteria below:
Toxicity remains (despite dose interruption) grade 3 or 4 or is clinically significant > 14 days	Discontinue study drug
Toxicity lasts 14 days or less and resolves to grade 2 or less or is no longer clinically significant	Reduce dose level per Table 1 and restart once toxicity has resolved to grade 2 or less or is no longer clinically significant
Grade 3 or 4 and/or clinically significant	
Not expected to be manageable/reversible with dose reduction	Discontinue study drug
Recurrence of Grade 3	Reduce one more dose level is available (see table 1), or if not discontinue study drug. NB note option of continuous dosing schedule as mentioned in 7.5

 Table 2.
 Dose modifications and discontinuation criteria for non-haematologic toxicities*

NCI CTCAE Toxicity Grade Action	
Recurrence of Grade 3 cardiac event ^a	Discontinue study drug
Recurrence of Grade 4	Discontinue study drug

* If the below specific recommendations for stomatitis/oral mucositis, hyperglycaemia, ILD/pneumonitis, ECG-changes and rash disagree with table 2 please follow the below not recommendations not table 2.

	Table 3.	Dose modifications and discontinuation criteria for haematological toxicitie
--	----------	--

NCI CTCAE toxicity grade	Action
Thrombocytopenia	
Grade 1, 2 or 3 (without bleeding)	None
Grade 3 (with bleeding) or grade 4	Hold study drug until it meets one of the criteria below:
Toxicity remains (despite dose interruption) grade 3 (with on-going bleeding episodes) or 4 > 14 days	Discontinue study drug
Toxicity lasts 14 days or less and resolves to grade 2 or less	Reduce dose level per table 1 and restart once toxicity has resolved to grade 2 or less
Neutropenia (NB GCSF is permitted as per local p	olicy)
Grade 1, 2 or 3	None
Grade 4	Hold study drug until it meets one of the criteria below:
Toxicity remains (despite dose interruption and GCSF) grade 4 > 14 days	Discontinue study drug
Toxicity lasts 14 days or less and resolves to grade 2 or less	Reduce dose level per table 1 and restart once toxicity has resolved to grade 2 or less or is no longer clinically significant

RBC transfusion is permissive and advised in the event of symptomatic anaemia or a haemoglobin falling below 80g/l. If anaemia occurs, an assessment of underlying causality should take place and non-IMP related causes considered.

Grade 4 neutropenia (neutrophil count < 0.5×10^{9} /l) should always be treated with GCSF according to local policy

Platelet transfusion should be used in the following situations:

- as treatment of a bleeding event with a platelet count $< 50 \times 10^{9}$ /l,
- platelets < 20×10^9 /l with concomitant infection
- platelets < 10×10^{9} /l in asymptomatic patients

If a toxicity is experienced for patients in the combination stage then the treating investigator should ascertain the causality of the toxicity to both IMPs:

- If at least possibly related to AZD2014 follow the dose modifications above.
- If related to rituximab, management and dose modifications of rituximab should be as per the local site or Investigators standard procedures.

Dose calculations for any weight changes should also be conducted as per local practice.

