- angioplasty
- vascular stent
- myocardial infarction
- angina pectoris
- congestive heart failure New York Heart Association Grade ≥2
- ventricular arrhythmias requiring continuous therapy
- supraventricular arrhythmias including atrial fibrillation, which are uncontrolled
- haemorrhagic or thrombotic stroke, including transient ischaemic attacks or any other central nervous system bleeding
- 10. Abnormal echocardiogram (ECHO) or multi-gated acquisition scan (MUGA) at screening (left ventricular ejection fraction [LVEF] <50%).
- 11. Torsade's de Pointes within 12 months of study entry.
- 12. Patients with uncontrolled diabetes Type I or uncontrolled Type II (HbA1c >7 mmol/L assessed locally) as judged by the local investigator.
- 13. Inadequate bone marrow reserve or organ function as demonstrated by any of the following laboratory values unless due to underlying NHL infiltration.
 - Absolute neutrophil count <1.5 x 10⁹/L (without GCSF / GMCSF support)
 - Platelet count <100 x 10⁹/L
 - Haemoglobin <90 g/L (transfusions permissible)

- Alanine aminotransferase (ALT) or aspartate aminotransferase (AST) >2.5 times the upper limit of normal (ULN) if no demonstrable liver involvement or >5 times ULN in the presence of liver involvement

- Total bilirubin >1.5 times ULN unless in the presence of Gilbert's syndrome with an elevated indirect fraction

- Serum creatinine >1.5 times ULN concurrent with creatinine clearance ≤50 mL/min (measured or calculated by Cockcroft and Gault equation); confirmation of creatinine clearance is only required when creatinine is >1.5 times the ULN

- 14. Current refractory nausea and vomiting, chronic gastrointestinal diseases, inability to swallow the formulated product or previous significant bowel resection or gastrointestinal disease that would preclude adequate absorption of AZD2014.
- 15. History of known hypersensitivity to active or inactive excipients of AZD2014 or drugs with a similar chemical structure or class to AZD2014.
- 16. Judgment by the Investigator that the patient is unsuitable to participate in the study and the patient is unlikely to comply with study procedures, restrictions and requirements.
- 17. Previous history of other active malignant disease other than fully excised basal or squamous cell carcinoma of the skin, carcinoma in situ of the uterine cervix or localised disease treated with curative intent using surgery alone, within the last 3 years.

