7.8 Concomitant Medication

7.8.1 Concomitant treatment with CYP inhibitors, inducers and substrates

If a patient requires short-term administration of a restricted CYP3A4/5, Pgp or BCRP **inhibitor** AZD2014 treatment must be withheld for three days prior to administration and not restarted until the concomitant therapy has been discontinued for the appropriate time period described in Appendix 2.

If a patient requires short-term administration of a restricted CYP3A4/5, Pgp (MDR1) or BCRP isoenzyme **inducer** this should be clearly documented in the Case Report Form (CRF) and may then be permitted, but the Investigator will be informed that this could lead to lower levels of study drug and a potential reduction in clinical efficacy.

If a patient requires short term administration of restricted **substrates** of OATP1B1, OATP1B3, MATE1 or MATE2K AZD2014 treatment must be withheld for 3 days prior to the first administration and not restarted until the concomitant therapy has been discontinued for the appropriate time period *described in Appendix 3*.

Information on all concomitant treatments given during the study with reasons for the treatment should be recorded in the CRF. If medically feasible, patients taking regular medication other than those excluded from this study should be maintained on it throughout the study period.

The lists of CYP inhibitors, inducers and substrates are not exhaustive and the absence of a drug from these lists does not imply that its combination with AZD2014 is safe.

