7.8.2 Other Concomitant Treatments

Information on any treatment pertinent to the inclusion/exclusion criteria in the 4 weeks prior to starting study treatment and all concomitant treatments given during the study with reasons for the treatment should be recorded. If medically feasible, patients taking regular medication, with the exception of potent or moderate inhibitors or inducers of CYP3A4/5 or CYP2C8, should be maintained on it throughout the study period.

- Patients who begin warfarin, or other vitamin K antagonists, therapy should be advised to have their anticoagulation monitored more frequently when receiving AZD2014 and should stop medication with AZD2014 at thrombocytopenia CTCAE Grade 3 or higher.
- Patients may continue to receive therapeutic bisphosphonates and erythropoietin preparations (e.g. Procrit, Epogen, Aranesp), if they were receiving them prior to beginning study treatment.
- Blood transfusions are allowed during the study.
- Other medication e.g. anti-emetics that are considered necessary for the patient's safety and well-being may be given at the discretion of the investigators.

Primary prophylaxis with anti-viral, anti-fungals and anti-Pneumocystis carinii pneumonia (*PCP*) medication are not required. These should be used according to local policy; however it should be noted that:

1. The systemic anti-Pneumocystis carinii pneumonia medication dapsone is **contraindicated** due CYP3A4/5 inhibitory effect.

2. Pentamidine **should NOT** be used for this indication due to its cardiac effects

Palliative radiotherapy to a site which does not contain a target lesion is permissible. Concomitant use of any other anticancer therapy, or moderate-to-significant inhibitors of CYP3A4 (Appendix 2), are prohibited.

Concomitant vaccination with live virus vaccines during rituximab treatment and for the duration the patient is peripherally depleted is prohibited.

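### The rule stopping AZD2014 at grade 3 thrombocytopenia covers patients who begin a vitamin K antagonist on trial but not those already taking one, whose written default is to continue

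*Protocol*

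**What the plan says.** Table 3 in Protocol section 7.5.1 sets the dose actions for thrombocytopenia. The row beginning "Grade 1, 2 or 3 (without bleeding" requires no action. Grade 3 with bleeding, or grade 4, requires a hold. The hold has two exits: discontinuation if the hold-level toxicity persists beyond 14 days, or restart at a reduced dose if it lasts 14 days or less and resolves to grade 2 or less.

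Section 7.8.2 adds a rule for anticoagulated patients. It is addressed to "Patients who begin warfarin, or other vitamin K antagonists, therapy". They are advised to have their anticoagulation monitored more often and "should stop medication with AZD2014 at thrombocytopenia CTCAE Grade 3 or higher". This rule has no bleeding condition.

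On medication already in use, section 7.8.1 says that "patients taking regular medication other than those excluded from this study should be maintained on it throughout the study period", and section 7.8.2 says that "patients taking regular medication, with the exception of potent or moderate inhibitors or inducers of CYP3A4/5 or CYP2C8, should be maintained on it". Both apply where medically feasible.

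Section 7.5 gives the treating physician latitude: "Dose reductions or holds and initiation of supportive care are allowed as clinically indicated by the treating physician". Section 7.9 lets the investigator stop treatment after any event judged to make it inadvisable.

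**The concern.** Section 7.8.2 reflects a judgement that grade 3 platelets on a vitamin K antagonist are reason enough to stop AZD2014, even without bleeding. That judgement does not depend on when the anticoagulant was started, but the rule does. A patient who entered the trial on warfarin falls outside it and back to Table 3, which requires nothing at non-bleeding grade 3. The advice on closer anticoagulation monitoring, in the same bullet, has the same limit.

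What is at stake is patient safety and consistency between sites. Two patients with the same platelet count on the same anticoagulant can be handled differently with both sites following the text.

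**Working it through.** No design figure is involved, so the check sets the provisions side by side.

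**Step 1. Can a patient already on a vitamin K antagonist enter?** Yes. No exclusion criterion in section 4.2 names one, nor does any entry in Appendix 2 or Appendix 3. Among supraventricular arrhythmias, a common reason for such treatment, exclusion 9 bars only "supraventricular arrhythmias including atrial fibrillation, which are uncontrolled". Section 7.8.1 warns that the drug lists are not exhaustive, but 7.8.2 itself provides for concurrent use, so the combination is not prohibited.

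**Step 2. Is *begin* just loose wording?** The text does not suggest so. The next bullet in 7.8.2, on bisphosphonates and erythropoietin, concerns patients who were receiving those drugs before study treatment. The section therefore distinguishes prior use from new use.

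**Step 3. Which written rule applies at non-bleeding grade 3?**

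| Patient | 7.8.2 stop rule | Table 3 | Written default |
|---|---|---|---|
| Begins the anticoagulant on trial | Applies | None | Stop, reading 7.8.2 as the specific rule |
| Already on it at entry | Does not apply | None | Continue, subject to 7.5 and 7.9 |

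**Step 4. Does another provision close the gap?** The precedence note in 7.5.1 opens "If the below specific recommendations for stomatitis/oral mucositis, hyperglycaemia, ILD/pneumonitis, ECG-changes and rash disagree with table 2", so it concerns Table 2 and named non-haematological toxicities. The mandatory stop list in 7.9 names neither thrombocytopenia nor anticoagulation.

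**Step 5. How long does the default run before the next required count?** Section 7.2 gives 8 dosing days per 28-day cycle at 2 x 125 = 250 mg a day. Section 7.3.1 schedules counts on days 1 and 15 in cycles 1-2, and on day 1 from cycle 3.

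- Cycles 1-2: 4 dosing days x 250 mg = 1,000 mg between counts.
- From cycle 3: 8 dosing days x 250 mg = 2,000 mg between counts.

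These amounts restate the schedule. They are not a measure of harm, and section 7.3 allows extra assessments in the event of toxicity.

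**Step 6. How can a Table 3 platelet hold end?**

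| State during the hold | Exit row met |
|---|---|
| Grade 2 or less within 14 days | Restart at reduced dose |
| Grade 4 beyond 14 days | Discontinue |
| Grade 3 with on-going bleeding beyond 14 days | Discontinue |
| Improved to grade 3 without bleeding by day 14, and staying there | Neither |

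Table 2 does not have this gap: its discontinue row covers grade 3 as well as grade 4 beyond 14 days.

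**The case against.** The strongest reply is that Tables 2 and 3 are described as guidelines and sit under a general instruction. Section 7.5 says substantial toxicities should be managed as medically indicated, with temporary suspension as appropriate, and 7.9 lets the investigator stop. This stands as far as it goes. A reader might infer that the protocol obliges sites to keep dosing these patients, and it does not. What is missing is a mandatory trigger. The authors did not leave patients who begin the anticoagulant to discretion alone, and the protocol gives no reason to treat prior users differently.

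A reader might also infer that Table 3 and 7.8.2 contradict each other for patients who begin the drug. There 7.8.2 reads naturally as the specific rule, and only a cross-reference is lacking.

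A third inference would be that the tolerability result is distorted, because delays in the first 2 cycles count under section 12.6. The protocol gives no rate from which to show this, and a discretionary hold can occur under any dosing table.

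On the hold exits, it is fair to say that drug is withheld meanwhile, which is the cautious state, and that the count may later recover or worsen. It would go too far to say the neutropenia rows share the gap. Their restart action also allows for toxicity that is no longer clinically significant, which can serve as an exit for a settled grade 3.

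**Conclusion.** The concern holds as a gap in a safety rule. For patients on a vitamin K antagonist at entry, the written default at non-bleeding grade 3 thrombocytopenia is to continue AZD2014, and only physician discretion stands against it. The conclusion rests on reading *begin* literally, which the neighbouring bullet supports, and on the absence of any exclusion of existing users. The number of patients affected cannot be estimated from the protocol, and no effect on the response endpoint or on the operating characteristics in section 12.6 is shown.

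The missing exit for a platelet hold that settles at non-bleeding grade 3 is real on the text but minor. A reader might conclude that Table 3 should simply force discontinuation at day 14. The protocol does not support that as the only answer: the same grade otherwise requires no action, and exclusion 13 waives the platelet limit when low counts are due to lymphoma infiltration, so some patients may be unable to reach grade 2.

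**What to change.** **Main change.** In section 7.8.2, replace *begin* with *are taking or begin*, and state that *stop* means hold. In the grade 3 platelet row of Table 3, add: *Exception: hold AZD2014 at grade 3 or higher in any patient taking a vitamin K antagonist (see 7.8.2).* This also extends the monitoring advice to existing users.

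**Secondary change.** Add an explicit exit to Table 3 for a platelet hold that improves to grade 3 without bleeding. Whether that is restart at a reduced dose or discontinuation is a clinical choice for the sponsor. It must respect the marrow-infiltration waiver in exclusion 13. Patients on a vitamin K antagonist should not restart at grade 3.

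**Cost.** The change needs a short amendment to one bullet and one table, with notice to sites. It will produce a few more holds, and those in cycles 1-2 count as delays in the tolerability assessment.

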7.5.2 Specific dose modification recommendations

7.5.2.1 Recommendations for Treatment of Nausea and Vomiting

In order to decrease the incidence of nausea and vomiting, an anti-emetic regimen should be used for patients, who are developing nausea after starting AZD2014 for the first time. On subsequent dosing days, the following antiemetics are recommended to be administered and continued daily throughout the AZD2014 dosing days.

Serotonin (5-HT3) antagonist (choose one from this list below):

- Dolasetron 100 mg by mouth daily
- Granisetron 2 mg by mouth daily or 1 mg by mouth twice a day

If nausea and vomiting are not being managed with the regimen above, start a breakthrough treatment with the addition of one agent of a different drug class, e.g.:

- Dexamethasone 8 mg PO at day 1 of the AZD2014 dosing period or
- Metoclopramide 10-40 mg PO or
- Olanzapine 5-10 mg PO or
- Promethazine (Phenergan)12.5 25 mg every 6 hours

on the AZD2014 dosing days prior to the AZD2014 dose.

If this is still not managing the nausea and vomiting sufficiently, add Lorazepam 0.5-2 mg by mouth or sublingual every 4 to 6 hours as needed, but only on the AZD2014 dosing days.

Should upper abdominal pain develop a H2 blocker or proton pump inhibitors can be added. For combinations, please refer to the manufacturers SMPC for the combination agent.

7.5.2.2 Recommendation for Treatment of Stomatitis/Oral Mucositis/Mouth Ulcers

For mild toxicity (Grade 1), use conservative measures such as non-alcoholic mouth wash or salt water (0.9%) mouth wash several times immediately after drug administration (1-3h) and during the day as required until resolution. AZD2014 treatment can be continued without a dose reduction.

For more severe toxicity (Grade 2 or 3), the suggested treatments are topical analgesic mouth treatments (i.e., local anesthetics such as benzocaine, butyl aminobenzoate, tetracaine hydrochloride, menthol, or phenol), with or without topical corticosteroids, such as triamcinolone oral paste 0.1% (e.g., Kenalog in Orabase®). Opioid analgesia (either intravenous, subcutaneous, or oral) is permitted. AZD2014 should be stopped until stomatitis improves to \leq Grade 1, and then resumed without a dose reduction. If Grade 2 to 3 stomatitis recurs, dose reduce AZD2014

Agents containing hydrogen peroxide, iodine, and thyme derivatives may worsen mouth ulcers. It is preferable to avoid these agents.

If the toxicity resolves or reverts to \leq CTCAE Grade 2 within 14 days of onset and the patient is showing clinical benefit, treatment with AZD2014 may be restarted, at the same dose or a lower dose, at the discretion of the Investigator.

If the toxicity does not resolve to \leq CTCAE Grade 2 after 14 days, then the patient should be withdrawn from the study and observed until resolution of the toxicity.

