7.9 Treatment discontinuation and Patient Withdrawal

In the event of discontinuation of study treatment, e.g. unacceptable toxicity or patient choice, full details of the reason/s for discontinuation should be recorded on the appropriate pages on the CRF. All patients, including non-compliant subjects, should be followed up according to the protocol unless they withdraw specific consent.

In the event of a patient's decision to withdraw from the trial, the Investigator should ascertain from which aspects of the trial the patient wishes to withdraw and record the details on the appropriate

CRF. If a patient chooses to withdraw from treatment only, the patient should discontinue treatment and continue to be assessed in accordance with the protocol.

If a patient wishes to withdraw from the trial (i.e. including trial specific assessments), but is willing for further data to be supplied to the Trials Office, then further routine "follow-up" data (e.g. disease status and survival) will continue to be supplied by the Investigator to the Trials Office. All information and blood/tissue samples collected up until point of retraction will be retained and analysed.

Patients who stop treatment due to AEs (clinical or laboratory) will be treated according to accepted medical practice and followed up as per protocol. All pertinent information concerning the outcome of such treatment must be recorded in the CRF.

The following are justifiable reasons for the Investigator to stop study treatment:

- unforeseen events: any event which in the judgement of the Investigator makes further treatment inadvisable
- serious violation of the study protocol (including persistent patient non-attendance and persistent non-compliance)
- stopping by the Investigator for clinical reasons not related to the study drug treatment

Patients must stop study treatment in the event of:

- SAE requiring permanent discontinuation of treatment
- the patient becoming pregnant
- Clinically significant ECG changes
- Interstitial lung disease
- Stevens-Johnson syndrome, Progressive multifocal Leukoencephalopathy or other significant infusion related reactions

If trial treatment is discontinued the patient must attend clinic for the end of treatment visit and 30 days (+/- 5 days) after their last trial treatment for the 30 days post treatment visit, unless they have withdrawn consent for these assessments.

End of treatment visit assessments

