12.1.2 Secondary outcome measures

- Best overall response rate post 6 cycles until the end of the trial, assessed using the revised Response Criteria for Malignant lymphoma (Appendix 1)
- Tolerability of AZD alone and in combination with rituximab will be assessed using Toxicities recorded during trial treatment using CTCAE v4.0
- Progression free survival is defined as the time from date of registration to the date of disease progression or date of death from any cause. Patients not reaching progression or death at the time of analysis will be censored at the last date they were known to be alive and progression free. Patients will be followed up for a minimum of 12 months.
- Overall survival time is defined as the time from date of registration to the date of death from any cause. Patients discontinuing the study, lost to follow-up or still alive at the end of the study will be censored at the date of last follow-up. Patients will be followed up for a minimum of 12 months. Duration of response is defined as the time from first documented response until relapse/progression, as determined by the Revised Response Criteria, or date of last follow up if relapse/progression free. Patients who die before a relapse/progression will be censored at their date of death.
- Maximum % decrease in the radiological SPD during the first 6 cycles will be assessed using the Revised Response Criteria for Malignant Lymphoma (Appendix 1) using the CT scan result collected at screening as a baseline value.

Exploratory Outcome Measures

- Correlation of response with pharmacodynamic biomarkers, cell of origin studies, lymphoidrelated mutational analysis and potential predictive biomarkers of response
- To determine the response to AZD2014 by PET CT criteria and analyse the effect of dual mTOR inhibition on PET signal / response when compared to standard CT response

Pre and post treatment biopsies (at subsequent relapse) will be performed to measure relative activity of the mTOR pathway in a biomarker exploratory analysis. Biopsies at relapse will be requested in patients within the rituximab stage to assess for evidence of synergy and mechanisms of resistance. On treatment biopsies on day 15 cycle 1 will remain optional.

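### Stomatitis at exactly Grade 2 falls under two restart rules (7.5.2.2), the rash examples include a drug that Appendix 3 restricts, and one withdrawal phrase conflicts with the follow-up rules

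*Protocol*

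**What the plan says.** **Stomatitis restart.** For Grade 2 or 3, protocol section 7.5.2.2 stops AZD2014 until improvement to at most "Grade 1, and then resumed without a dose reduction. If Grade 2 to 3 stomatitis recurs, dose reduce AZD2014". A later paragraph of the same section begins "If the toxicity resolves or reverts to" Grade 2 or less within 14 days of onset, and goes on: "and the patient is showing clinical benefit, treatment with AZD2014 may be restarted, at the same dose or a lower dose", at the investigator's discretion. The footnote to Table 2 in section 7.5.1 reads "If the below specific recommendations for stomatitis/oral mucositis, hyperglycaemia, ILD/pneumonitis, ECG-changes and rash disagree with table 2 please follow" the specific text, so Table 2 gives way to section 7.5.2.2.

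**Stomatitis not at Grade 2 or less after 14 days.** Section 7.5.2.2 says "then the patient should be withdrawn from the study and observed until resolution of the toxicity". Table 2 has a row for the same situation, "Toxicity remains (despite dose interruption) grade 3 or 4 or is clinically significant > 14 days", and its action is to stop study drug. Section 7.9 says: "Patients who stop treatment due to AEs (clinical or laboratory) will be treated according to accepted medical practice and followed up as per protocol". Section 7.10 follows all patients for at least 1 year or until death. The overall survival definition in section 12.1.2 says: "Patients discontinuing the study, lost to follow-up or still alive at the end of the study will be censored" at last follow-up.

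**Rash.** Section 7.5.2.3 lists fexofenadine among its example oral antihistamines. Appendix 3 lists it as a restricted OATP1B1/1B3 substrate, with a washout of five terminal half-lives. Section 7.8.1 requires AZD2014 to be withheld for 3 days before such a drug is first given and until its washout is complete.

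**Use in the analysis.** Section 12.6 scores a patient as not tolerating treatment if a toxicity leads to a treatment delay or dose modification in the first 2 cycles. The marks are 10 of the first 15 and 21 of 30 for monotherapy, and 2 of the first 3 and 4 of 6 for the combination.

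**The concern.** These are instructions that sites act on. A site that takes up the fexofenadine example either gives a restricted drug alongside AZD2014 or has to hold AZD2014, possibly for a Grade 1 or 2 rash on which Table 2 takes no action.

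The two stomatitis rules let sites treat the same patient differently. Because tolerability is scored from delays and dose changes, part of that count would then reflect which paragraph a site followed. Section 1.2.3.2 names mucositis among the most frequently reported events and among those most commonly leading to interruption, so the situation is foreseeable.

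The withdrawal wording puts at risk follow-up that the protocol elsewhere intends to keep, and it would do so for a toxicity-related reason.

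**Working it through.** **1. Where the two stomatitis rules overlap.** Call the hold-to-Grade-1 paragraph rule A and the later paragraph rule B.

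| Current grade | Rule A | Rule B (within 14 days, clinical benefit) |
|---|---|---|
| 1 or less | Resume, same dose | May restart, same or lower dose |
| 2, fallen from 3 | Hold | May restart, same or lower dose |
| 2, began at 2 | Hold | Threshold already met |
| 3 | Hold | Not met |

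The hold-or-restart conflict is at exactly Grade 2. Rule B's verbs fit a fall from Grade 3 best, but its threshold is also met by stomatitis that began at Grade 2. The Table 2 footnote ranks section 7.5.2.2 above Table 2 and does not rank A against B.

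Two gaps follow. A patient still at Grade 2 on day 14 stays on hold under rule A with no end point, and the 14-day withdrawal does not apply because Grade 2 satisfies it. Rule A does not cover Grade 4.

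**2. Effect on one patient's score.** Take Grade 3 on day 3 and Grade 2 on day 8, a dosing day. Rule A withholds days 8 and 9, a delay, so the patient is not tolerable. Rule B at 125 mg bd gives no delay, so the patient is tolerable on this event. Rule B at 100 mg bd is a dose modification, so not tolerable.

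**3. Effect on the tolerability conclusion, given one such patient.** Write b(x; n, p) for the binomial probability of x tolerable patients among n. First, the plan's own figures: the probability of passing is the sum over x = 10 to 15 of b(x; 15, p) × P(Y ≥ 21 − x), with Y binomial(15, p).

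- p = 0.80: 0.905 (protocol 90.4%).
- p = 0.60: 0.152 (protocol 15.3%); early stop 0.597 (protocol 59.7%).

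Now let one patient's score be open, and apply the 10-of-15 rule strictly.

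- Patient in the second 15: the result changes if at least 10 of the first 15 tolerate and the other 29 contribute exactly 20. Sum over x = 10 to 15 of b(x; 15, p) × b(20 − x; 14, p).
- Patient in the first 15, with x tolerable among the other 14 and y among the second 15: the result changes if x = 9 and y ≥ 11, or if x ≥ 10 and x + y = 20.

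| True rate | Second 15 | First 15 |
|---|---|---|
| 80% | 4.4% | 10.4% |
| 70% | 11.8% | 18.8% |
| 60% | 7.2% | 9.8% |

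For the combination's 4-of-6 mark, ignoring the check after 3 patients, the result changes if exactly 3 of the other 5 tolerate: 10 × p³ × (1 − p)² = 20.5%, 30.9% and 34.6% at 80%, 70% and 60%. All these figures are conditional on an affected patient.

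**4. Fexofenadine against the dosing calendar.** AZD2014 is given on days 1, 2, 8, 9 and so on. From the day 2 evening dose, 72 hours of withholding ends on the evening of day 5. From then to the day 8 morning dose is 60 hours, which must hold both the fexofenadine course and five half-lives. The protocol gives no half-life. At assumed values of 6, 12 and 24 hours the washout is 30, 60 and 120 hours, leaving 30 hours, none, and a shortfall. Anything beyond a very short course costs a dosing day.

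**5. The withdrawal wording.** Section 7.9 separates withdrawing from treatment only from withdrawing from the trial. Table 2 uses the first sense and section 7.5.2.2 the second. Read literally, section 7.5.2.2 meets the censoring condition in section 12.1.2. Read with sections 7.9 and 7.10, the patient stays in follow-up.

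**The case against.** **Rule B can be read as an exception to rule A.** It is permissive, at the investigator's discretion, and needs clinical benefit. The first response CT comes after cycle 2 (section 7.3.4), so within the tolerability window benefit would be judged clinically and rule B would seldom be used. Section 7.5 also leaves holds and reductions to the treating physician. This stands as a limit on frequency. It does not tell a site which rule governs at Grade 2, or what to do on day 14.

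**The tolerability marks are not rigid.** Section 12.4 makes the 15-patient rule guidance only and leaves expansion of the combination stage to the safety committee. A reader might infer that the restart conflict undermines the tolerability conclusion. The documents do not support that: the outcome is secondary, the number affected is not given, and the percentages apply only if such a patient occurs.

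**A reader might infer that the withdrawal phrase would censor overall survival.** Section 7.9 keeps patients who stop for adverse events in follow-up, and section 7.10 follows everyone for at least a year or until death. Early censoring arises only if a site takes the phrase literally against those sections. The trigger should also be rare: section 1.2.3.2 describes these events as generally reversible within 1 week of stopping the drug.

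**Fexofenadine is only one example.** Loratadine, cetirizine and others are listed, section 7.8.1 already governs restricted drugs, and section 1.2.3.2 reports no rash so far on intermittent dosing. Nobody is forced to use it. It remains wrong to suggest, without warning, a drug that another section restricts.

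**Conclusion.** The three inconsistencies are in the current text and should be corrected. The matter is minor to moderate. The fexofenadine mismatch is plain and rests on no assumption; only the cost in dosing days depends on an assumed half-life. The stomatitis conflict is confined to exactly Grade 2, whether the toxicity began there or fell from Grade 3. It can change a patient's tolerability score, and for one such patient the 21-of-30 conclusion changes with probability 4.4% to 18.8% at true rates of 60% to 80%, assuming the interim rule is applied strictly and patients are independent. How often such a patient arises is unknown and probably small. The withdrawal wording conflicts with Table 2 and with sections 7.9 and 7.10; it could lead to early censoring of overall survival but need not. The primary outcome and its 9-of-30 rule are not touched.

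**What to change.** 1. **Rash (7.5.2.3):** delete fexofenadine. Other antihistamines are already listed.
2. **Stomatitis restart (7.5.2.2):** keep the first rule, which is to hold at Grade 2 or 3, restart at Grade 1 or less at the same dose, and reduce on recurrence. Confine the later restart paragraph to Grade 4, or delete it so that Table 2 applies to Grade 4. State the action for a patient still at Grade 2 on day 14. The clinical team should confirm the choice.
3. **Withdrawal (7.5.2.2):** replace the phrase with *withdrawn from study treatment; follow-up continues per sections 7.9 and 7.10*.

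The cost is a wording amendment and a memo to sites, with no change to sample size or analysis. Section 7.5 still gives physicians discretion over holds and reductions, so some variation between sites in the tolerability count will remain.
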